Patient with comorbidities including cardiac disease, chronic hypertension, any stage kidney disease (including abnormal creatinine level) and use of diuretics.

Patients undergoing extensive ureterolysis

Blood loss more than 500 mls

Contra-indications to position change and insufflation

Study design:

Prospective randomized controlled study 2X2 bloc randomized based on position status and Patient position as **the two interventions** being evaluated:

- 1. Patient Position: flat versus Trendelenburg
- 2. Insufflation status: Yes versus no insufflation.

Outcomes:

Primary outcome: Time in seconds to satisfactorily complete a cystourethroscopy (visualize the dome, the ureteral jets, the bladder mucosa scan and the urethra).

With additional detail in recording time as follows

T0: Start of cystoscopy

T1: time to see one of the ureteral jets

T2 as the second ureteral jet T3: completion of cystoscopy

Exploratory outcome:

Surgeon satisfaction with the interventions (Likert scale questionnaire): The surgeon completes 6 Likert scale questions:

1- Global satisfaction (I will use this method routinely; it satisfies my requirements for cystoscopy).

Randomization

The randomization scheme is maintained by Redcap electronically at the time of consent.

Patients are randomized to 1 of 4 groups based on position and insufflation status

- 1- Position flat, No insufflation,
- 2- Position Trendelenburg, insufflation to 15 mm Hg
- 3- Position Flat, insufflation
- 4- Position Trendelenburg, No insufflation

Randomization occurs in preOp prior to rolling to the operating room.

Neither the surgeons nor the operating room team are blinded to the study group as it required changing position and insufflation.

Cystoscopy medium is sterile water.

#UTHealth Houston IRB NUMBER: HSC-MS-22-1081 IRB APPROVAL DATE: 02/28/2023 Randomization will be performed by the research team (the research fellow who is part of the research team).

It will be performed via redcap using the permutated block method, with an allocation ratio of 1:1:1:1. Patients are blinded to what group they are randomized to.

If cystoscopy is not completed and additional dye is necessary for visualization (as would normally occur outside the setting of the study), then, subjects will be treated as per routine and receive sodium fluorescein (25 mg intravenous sodium fluorescein (concentration 500 mg in 5 mL).

Time will be recorded by the circulating nurse via a stopwatch.

Study duration:

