Continuous variables are described with mean (SD) or median (range) depending on the distribution of the data. Statistical tests for continuous data were based on 1-way analysis of variance for normally distributed data, or the Kruskal-Wallis test for nonnormal data. This is determined by histogram plots and Levene test. Categorical variables are described with numbers (percentages) and compared using the χ^2 test. All statistical tests were 2-tailed, and were based on the intent-to-treat principle.

Sample size analysis

Median and IQR cystoscopy duration is 168 (86-286) seconds⁸, a clinically significant improvement in cystoscopy times would be 108 (69-160).

	Insufflation -	Insufflation +
Flat	Group1	Group2
T-Berg	Group3	Group4

Using analysis of variance, 28 subjects in each arm for a total of 112 subjects would be needed to detect an effect size of > 60 seconds, with 80% power and a 2-tailed alpha of 0.05 to achieve statistical significance using the frequentist method. To account for 20% drop outs, we will include 34 patients in each group for a total of 136 cystoscopy procedures,

The one minute decrease in operative time is used based on prior studies showing that the use of "Lasix" intraoperatively can significantly reduce cystoscopy duration by about 78 seconds.⁸

- CONSORT diagram will be performed
- We will evaluate for the presence of interaction between the different interventions as two interventions are employed at the same time.
- Intention to treat analysis will be performed
- All unadjusted outcomes will be reported descriptively (mean SD/ median IQR)
- For all outcomes, we will conduct intent-to-treat Bayesian analysis to calculate probabilities of intervention benefits and harms. We will use neutral priors and exclude large treatment effects. We will report posterior medians of group differences, their corresponding 95% credible intervals, and probability of treatment benefit.

Funding:

IRB NUMBER: HSC-MS-22-1081
IRB APPROVAL DATE: 02/28/2023

None

OVERSIGHT RESPONSIBILITIES

Oversight of the trial is provided by the Principal Investigator (PI), [name] and Co-investigators Drs [name] and [name].

Ethics

- IRB approval will be sought for this study, and admin Approval sought from Harris Health and MHH approval as well as a departmental review.

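### For a 2x2 trial the plan names only one-way tests for time to completion and does not say whether they run by factor or across four groups; one pre-specified two-way model with named contrasts would answer the stated question

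*Combined protocol and SAP*

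**What the plan says.** The Study design section describes a "Prospective randomized controlled study 2X2 bloc randomized based on position status", and the Randomization section adds: "Patients are randomized to 1 of 4 groups based on position and insufflation status", in a 1:1:1:1 ratio. The main objective, under General Information, is to find out which intervention or combination is the more efficient. The Hypothesis section names both factors without saying whether their effects are meant separately or jointly. The primary outcome is time in seconds from start (T0) to completion (T3).

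For continuous data the Statistical analysis section says: "Statistical tests for continuous data were based on 1-way analysis of variance for normally distributed data, or the Kruskal-Wallis test for nonnormal data". The choice between the two tests is made on the data: "This is determined by histogram plots and Levene test". No contrast, pairwise comparison or factor term is named.

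The Sample size analysis section adds three relevant statements:

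- On size: "Using analysis of variance, 28 subjects in each arm for a total of 112 subjects would be needed to detect an effect size of" more than 60 seconds. It does not say one-way or two-way, or which comparison the 60 seconds refers to.
- On interaction: "We will evaluate for the presence of interaction between the different interventions as two interventions are employed at the same time".
- On the Bayesian analysis: "For all outcomes, we will conduct intent-to-treat Bayesian analysis to calculate probabilities of intervention benefits and harms", followed by "We will report posterior medians of group differences, their corresponding 95% credible intervals, and probability of treatment benefit". The groups to be differenced are not identified.

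**The concern.** The objective needs three kinds of result: the effect of each factor, whether one factor's effect depends on the other, and how the four combinations compare. The named tests deliver at most part of this.

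A significant omnibus result across four groups is compatible with position acting alone, insufflation acting alone, both acting, or a single cell standing apart. Two by-factor tests would give the main effects but say nothing about combinations. The interaction and Bayesian statements could fill the gap, but with no model and no named comparisons, how they fill it could be decided after the data are seen. At stake is whether the trial's main conclusion rests on a comparison fixed in advance.

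**Working it through.** **Inputs.** From the Sample size analysis section: median (IQR) 168 (86-286) s and 108 (69-160) s, target 60 s, 28 per arm (34 with dropout), 80% power, two-sided alpha 0.05. No SD is stated. Assumption: SD = IQR/1.349.

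- (286 - 86)/1.349 = 148.3 s
- (160 - 69)/1.349 = 67.5 s
- Root mean square of the two: 115.2 s

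Both sets of quartiles are right-skewed, so these SDs are rough.

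**Does the plan's own sample size show which analysis was meant?** Two different routes come within one patient per arm of 28.

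- Pooled main effect, SD 115.2: n per cell = (1.960 + 0.842)² x 115.2²/60² = 28.9, so 29. Power at 28 per cell is 0.78.
- Four-group omnibus F, SD 67.5, means 0, 30, 30, 60: 29 per arm. Power at 28 is 0.79.

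The omnibus F at SD 115.2 does not reproduce 28. It needs 42 per arm if one factor acts, 55 if one cell differs, and 82 if two cells are 60 s apart with the others midway. The sample size therefore does not settle by-factor against four-group.

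**What each test can detect.** Noncentral F, 28 per arm, 108 error df, SD 115.2. Omnibus noncentrality = n x sum of squared deviations of the cell means/SD². Main-effect noncentrality = n x effect²/SD².

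| True pattern (60 s) | Omnibus, 3 df | Main effect, 1 df |
|---|---|---|
| One factor acts | 28 x 3600/115.2² = 7.60; power 61% | 7.60; power 78% |
| Both factors act | 28 x 7200/115.2² = 15.2; power 91% | 7.60; power 78% each |
| One cell differs | 28 x 2700/115.2² = 5.70; power 48% | effect 30 s, 1.90; power 28% each |

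Neither approach is uniformly stronger.

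**Skewed data.** Under the plan's rule, skewed times go to Kruskal-Wallis, so the 61% v 78% row is not the comparison that would apply. I simulated lognormal times with one factor multiplying the median by 108/168, 28 per arm, and log SD 0.62/0.77/0.89. The outer values come from the plan's quartiles. Power, to within a point or two of simulation error:

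- Four-group Kruskal-Wallis: about 87/69/55%
- Kruskal-Wallis on one two-level factor: about 96/84/72%
- Two-way model in seconds, robust standard errors, main effect: about 92/74/57%
- Two-way model in log seconds, main effect: about 96/85/74%

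**Interaction and cell contrasts.** The difference of differences has variance 4 x SD²/n, so for 60 s the noncentrality is 7.60/4 = 1.90 and power is 28%. At SD 67.5 and 148 s it is 65% and 19%. At 34 per arm and SD 115 it is 33%. The 95% CI half-width at SD 115 is about 43 s for a main effect, 86 s for the interaction, and 43 x √2 = 61 s for a difference between two cells. A 60 s difference between two cells has about 50% power (91% to 33% over the SD range).

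**The case against.** The strongest reply is that the plan never says the one-way tests run across four groups. It calls position and insufflation the two interventions, and a one-way test of flat against Trendelenburg is a test of the position main effect. One route to the stated sample size is exactly that comparison. The plan also promises to evaluate interaction and to report group differences with credible intervals, which are effect estimates rather than omnibus p-values. And the time scale is not absent: the outcome is defined in seconds and the target is 60 seconds.

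Most of this stands. A reader might infer that the plan has no means of estimating a position or insufflation effect, or that it ignores interaction. The documents support neither reading. What remains is that by-factor or four-group is not stated, that no named test yields an interaction or compares combinations, and that the Bayesian differences have no named groups. On scale, what is open is mean, median or log time.

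A reader might also infer a large power gain from the 61% v 78% comparison. That is normal-theory ANOVA with one factor acting. Against four-group Kruskal-Wallis on skewed times the gain in seconds is only a few points, and Kruskal-Wallis by factor has more power than the model in seconds.

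**Conclusion.** The point holds as a cheap improvement. The named tests, on either reading, do not answer the whole of the stated objective, and the statements that might do so specify neither a model nor the comparisons. A two-way factorial model answers it directly.

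The benefit is interpretive. Power may rise or fall: the omnibus test is the stronger one when both factors act (91% v 78%) or when only one cell differs (48% v 28%). Nor do the documents establish that seconds must be the primary scale. Under a lognormal, multiplicative assumption log time has more power, while seconds matches the outcome definition and the 60 s target.

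The figures rest on SDs inferred from quartiles (67.5 to 148 s), on 28 analysed per arm and, for the simulations, on equal log SDs in all cells. The conclusion about specification does not depend on them.

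**What to change.** For time to completion (T3 - T0), replace the one-way/Kruskal-Wallis rule with one pre-specified two-way model containing position, insufflation and position x insufflation.

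- **Report, whatever the interaction result:** each main effect averaged over the two levels of the other factor, the interaction, the four cell estimates, and named cell contrasts (for example flat without insufflation against each other cell), all with 95% CIs.
- **Bayesian analysis:** use the same contrasts.
- **Scale:** choose seconds or log seconds before data are seen, and keep the other as a sensitivity analysis. The choice affects the interaction slightly. If both factors act multiplicatively with equal log SDs, an ordinary interaction test in seconds rejects about 6-10% of the time, against about 5% on log time.
- **Alpha:** state the rule for the two main effects. Splitting it (0.025 each) lowers main-effect power from 78% to 69% at SD 115.
- **Coding:** define cells by position and insufflation, not by group number. The Randomization list and the sample-size table number groups 2, 3 and 4 differently and must be reconciled.

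The cost is analysis wording only, with no added patients or data. The main downside is the low power for the interaction: a non-significant result must not be read as no interaction. The cell contrasts are also imprecise and should be read through their intervals.

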Trendelenburg, abdominal insufflation and time to completion of cystoscopy. A prospective randomized trial.

NCT05786391

Version Date: 02/28/2023

Protocol Title: Trendelenburg, abdominal insufflation and time to completion of cystoscopy. A prospective randomized trial.

Principal investigator: [name] (Gynecology Faculty)

Statistician: [name]

Study coordinator: [name]

Population: 136 female patients undergoing a planned cystoscopy after Minimally

Invasive Gynecological procedure.

Number of sites: Two sites MHH-TMC and LBJ.

Study duration: 2 years

Subject duration: 6 weeks

General Information (PICO)

This is a randomized controlled trial assessing time to completion of cystoscopy in seconds after minimally invasive gynecologic surgery

We seek to compare the efficiency of the cystoscopy with two interventions: after two interventions:

- 1- patient position during the cystoscopy (Trendelenburg (head down) or flat)
- 2- Abdominal insufflation (insufflation versus no insufflation).

Both interventions are used as usual care and depend on surgeon preference without evidence why one would faster at completing the cystoscopy. Also note that these two interventions are performed multiple times during the surgery itself and outside the cystoscopy procedure routinely.

Our main objective is to assess which intervention or combination of interventions is more efficient

Background

latrogenic injury to the genitourinary tract is a rare, but significant cause of morbidity in patients undergoing gynecologic surgery for benign indications.1–3 In 2012, the American Association of Gynecologic Laparoscopists recommended that routine cystoscopy be performed after all laparoscopic hysterectomies, whereas the American College of Obstetricians and Gynecologists limited the endorsement to prolapse and incontinence procedures.4,5 Universal cystoscopy, where all women undergoing hysterectomy undergo cystoscopy, has been advocated because as many as 75% of genitourinary injuries occur in women without identifiable risk factors.

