#UTHealth Houston IRB NUMBER: HSC-MS-22-1081 IRB APPROVAL DATE: 02/28/2023 In one large study, cystoscopy was associated with a median increase in operative time of 17 minutes⁶. Increases in operative time and cost are the most commonly cited concerns regarding cystoscopy with recent estimates of operating room time, not including surgeon and anesthesiologist fees, at \$37 per minute,⁷ cystoscopy results in an additional \$629 per hysterectomy in operating room time alone.

When performing gynecologic laparoscopy, the patient is in a Trendelenburg position (Head down) and the abdomen is normally insufflated to 15 mm Hg during the entire surgery that can take up to 4 hours.

Cystoscopy is done at the end to assure integrity of the bladder and ureteral function, Some surgeons like to do it with the patient in the Trendelenburg position and others flatten the patient position or insufflate the abdomen with the thought that it may reduce the time needed to complete the cystoscopy.

Theoretically, one would predict that performing the cystoscopy under low intraabdominal pressure (no CO2 insufflation) and flat (with the added effect of gravity), would save time in the operating room.

In addition to those modifiable factors, additional factors may include fluid status (total urinary output during the surgery and fluid given intraoperatively as well as blood loss), duration of the surgery, manipulation of the ureters and the bladder (ureterolysis or bladder mobilization/presence of scar tissue) as well as blood loss overall.

Hypothesis:

Non Trendelenburg or flat position and Non insufflation of the abdomen significantly reduces cystoscopy procedure time after gynecologic laparoscopy.

Objective:

We seek to compare the efficiency of the cystoscopy with two interventions: after two interventions:

- 1- patient position during the cystoscopy (Trendelenburg (head down) or flat)
- 2- Abdominal insufflation (insufflation versus no insufflation).

Population

All patients undergoing minimally invasive gynecologic surgery with planned cystoscopy to evaluate urinary tract injury at two main sites: LBJ and MHH-TMC

Inclusion:

Patient undergoing Planned cystoscopy in the benign gynecology service.

Exclusion:

Pregnancy Known urologic anomaly Unplanned cystoscopy

> #UTHealth Houston IRB NUMBER: HSC-MS-22-1081 IRB APPROVAL DATE: 02/28/2023

Cancer surgery

Urogynecology surgery

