Study duration will be for 6 weeks to allow to review the chart for postoperative outcomes, see variable list to be collected.

Adverse events:

None anticipated outside the routine procedure of cystoscopy.

Cystoscopy risks include possible urinary tract infection. Participation in the study does not increase the risk, as cystoscopy is planned.

There are no additional risks involved with this study beyond the risks discussed at the time of surgical consent. Both position changes (Trendelenberg) and insufflation are part of the laparoscopic procedure. This means that if a patient has a contra-indication to any intervention, she will not be undergoing the procedure. The cystoscopy portion of the procedure is expected to take minutes, in comparison to the procedure, which will take hours. Risks of insufflation and position changes include hemodynamic and respiratory changes that are closely monitored by the anesthesia and the surgical team. We have included this in the consent form.

Data:

Demographic characteristics are abstracted from chart review by study personnel. Characteristics included age, BMI, parity, race/ethnicity, indication for surgery, and medical history. Intervention and surgical data are collected, including type of surgery, surgical start and stop times, cystoscopy start and stop times, estimated blood loss, and whether furosemide or an intravenous fluid bolus was given to assist with assessment of ureteral jets.

Cystoscopy is performed using a 21F sheath and a 70-degree cystoscope. Per protocol, after determining the 12 o'clock position at the bladder dome via the air bubble, the ureteral jets were visualized until surgeon's confidence in the patency of the ureters was determined. Subsequently, a systematic global survey was performed of the bladder, followed by examination of the urethra as the cystoscope was withdrawn.

There are no anticipated adverse events for the two interventions evaluated, as the patient position and insufflation are two variables that routinely occur during surgery.

#UTHealth Houston IRB NUMBER: HSC-MS-22-1081 IRB APPROVAL DATE: 02/28/2023

At the conclusion of the study (when the final randomized patient met the 6-week postoperative mark), all patient medical records will be reviewed for operative data including operative complications.

Statistical analysis

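### The named tests of cystoscopy time use neither site nor BMI; a prespecified model adjusted for both is a cheap refinement with a probably modest gain, not the repair of an error

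*Combined protocol and SAP*

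**What the plan says.** The Statistical analysis section gives the tests for continuous outcomes: "Statistical tests for continuous data were based on 1-way analysis of variance for normally distributed data, or the Kruskal-Wallis test for nonnormal data". The primary outcome, cystoscopy time in seconds, falls under this sentence. No site term or covariate is mentioned.

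The bullets at the end of the Sample size analysis section add an evaluation of interaction and a Bayesian analysis of all outcomes, but list model terms for neither. One bullet promises a descriptive report of unadjusted outcomes, which hints at an adjusted counterpart; none is defined.

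The header gives "Number of sites: Two sites MHH-TMC and LBJ". The Randomization section describes permuted blocks at 1:1:1:1, mentions no stratification by site, and fixes the timing: "Randomization occurs in preOp prior to rolling to the operating room". It adds: "Neither the surgeons nor the operating room team are blinded to the study group".

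Under Data, BMI is among the baseline items: "Characteristics included age, BMI, parity, race/ethnicity, indication for surgery, and medical history". Type of surgery appears in a separate list: "Intervention and surgical data are collected, including type of surgery, surgical start and stop times". The Background names other possible influences on cystoscopy time: "additional factors may include fluid status (total urinary output during the surgery and fluid given intraoperatively as well as blood loss", followed by surgery duration and manipulation of the ureters and bladder.

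**The concern.** The outcome is widely spread (the quoted reference IQR is 86 to 286 s) against a target difference of 60 s, with 28 evaluable patients per arm. Site and BMI are both known before allocation. If they predict cystoscopy time, leaving them out gives wider intervals and lower power than the same patients could provide.

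A second reason does not depend on how prognostic they are. The word unadjusted implies that adjusted results may follow, and no covariate list is fixed. Covariates could then be chosen after the data are seen, and some candidates that the protocol itself mentions arise during surgery, under a team that knows the allocation.

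**Working it through.** **Inputs from the Sample size analysis section.** 28 per arm (112 in total), a 60 s difference, two-sided alpha 0.05, 80% power; reference median 168 s (IQR 86–286), target 108 s (IQR 69–160).

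**Assumptions, because the documents give no SD and no R².** SD = IQR/1.349:

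- reference: (286 − 86)/1.349 = 148.3 s
- target: (160 − 69)/1.349 = 67.5 s
- pooled: √((148.3² + 67.5²)/2) = 115.2 s

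**The plan's own figure.** With no SD or pattern of means stated, 28 per arm cannot be tied to one calculation. For a 60 s main effect of one factor at SD 115.2 s, the noncentrality is (112/4) × 60²/115.2² = 7.60. On 1 and 108 df this gives 78.0% power, close to the planned 80%. The four-group F test has the same noncentrality (28 × 4 × 30²/115.2² = 7.60) but spreads it over 3 df, and its power is 61.2%. That gap comes from the choice of contrast and has nothing to do with covariates.

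**Adding site and BMI (2 covariate df).** The residual variance becomes SD² × (1 − R²). Chance imbalance between arms inflates the variance of the effect; over 5,000 simulated designs with covariates independent of arm, the mean inflation is 1.019. Error df fall to 106. The noncentrality is therefore about 7.60/((1 − R²) × 1.019), and power is averaged over the simulated designs. The 95% CI half-width is about 1.983 × 115.2 × √((1 − R²) × 1.019 × 4/112); unadjusted it is 43.1 s.

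| R² | Noncentrality | Power, main effect | CI half-width |
|---|---|---|---|
| unadjusted | 7.60 | 78.0% | 43.1 s |
| 0 | 7.46 | 77.2% | 43.6 s |
| 0.05 | 7.85 | 79.3% | 42.5 s |
| 0.10 | 8.29 | 81.4% | 41.3 s |
| 0.20 | 9.32 | 85.7% | 39.0 s |

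Break-even is where (1 − R²) × 1.019 = 1, so R² = 1 − 1/1.019, or about 0.02.

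**Adding type of surgery as well (4 covariate df, assuming three categories).** Mean inflation rises to 1.039 and break-even to about 0.04. Power at the same four values of R² is 76.4, 78.5, 80.6 and 85.0%. The extra terms pay only if they raise R².

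**Sensitivity to the SD (2 covariate df, same four values of R²).**

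- SD 148.3 s: 56.5% unadjusted; 55.7, 57.8, 60.1 and 65.2% adjusted.
- SD 67.5 s: above 99% throughout.
- Log time: difference ln(168/108) = 0.442; log SDs ln(286/86)/1.349 = 0.891 and ln(160/69)/1.349 = 0.623; pooled 0.769. Power is 85.4% unadjusted; 84.7, 86.5, 88.2 and 91.6% adjusted.

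**Choice of scale.** Both quoted IQRs are right-skewed: 168 − 86 = 82 s below the median against 286 − 168 = 118 s above it, and 39 s against 52 s. The log scale also brings the two spreads closer, from a ratio of 148.3/67.5 = 2.2 to 0.891/0.623 = 1.4.

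**The case against.** The strongest reply is that nothing is wrong. Adjusted and unadjusted analyses are both legitimate, and randomization protects the unadjusted one. A reader might infer that leaving site out biases or invalidates the comparison; the documents do not support that.

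Nor do they show that site or BMI predicts cystoscopy time. The factors that the Background names mostly arise during surgery. Some exclusions, such as kidney disease and diuretic use, may already narrow the variation. The exclusion "Patients undergoing extensive ureterolysis" and the one for blood loss above 500 mL are less clear-cut: they become known only after preoperative allocation, and the analysis is by intention to treat. For R² between 0 and 0.05, adjustment moves power by −0.8 to +1.3 points, and the unknown SD matters far more. This stands, and it is why the point is only a refinement.

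Three further objections also stand and shape the fix:

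- Kruskal-Wallis takes no covariates, so terms cannot simply be added to the existing plan.
- Choosing log time only if the data look skewed would be another data-dependent decision.
- Type of surgery is listed with the surgical data. A reader might take it for a ready baseline covariate, but nothing says that the planned procedure is recorded before allocation.

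Finally, the plan might be read as ruling out adjustment altogether. It does not: the Bayesian and interaction models are unspecified, so the point is limited to the named frequentist tests.

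**Conclusion.** The point holds as a low-priority improvement. The named tests omit site and BMI, both available before allocation, and the unadjusted comparison remains valid. At an assumed SD of 115 s with 28 per arm, adjusting for both costs 0.8 power points if they explain nothing (78.0% to 77.2%). It gains 1.3 points at R² = 0.05, 3.4 at 0.10 and 7.7 at 0.20. That the gain is modest is a judgement, because the documents give no R².

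It would be wrong to credit adjustment with lifting power from 61% to 78%: that is the difference between a four-group test and a 1-df main effect, and is a separate matter. What does not depend on R² is the value of fixing the covariates, or stating that there are none, before the data are seen.

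**What to change.** Replace the ANOVA/Kruskal-Wallis choice for cystoscopy time with one prespecified primary linear model:

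- Fix the scale in advance. Log time is reasonable; report effects as ratios and also in seconds.
- Include position, insufflation, their interaction, site and BMI (2 covariate df). Code the two factors ±½ so that each main effect is an average over the other factor.
- Report the unadjusted result alongside, and use the same covariates in the Bayesian model.
- Add type of surgery only if the planned procedure is recorded before randomization, in a few categories named in the SAP.
- Keep blood loss, surgery duration, furosemide and fluid bolus out of the primary model, because they arise after allocation.

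If no adjustment is intended, one sentence saying so closes the point. The cost is SAP wording, plus one preoperative data field if type of surgery is used. The statistical downside is the loss of 0.8 power points shown above, or 1.6 points (78.0% to 76.4%) with 4 covariate df, if the covariates explain nothing.

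### The rule that chooses between ANOVA and Kruskal-Wallis uses Levene's test, a variance test, as its only formal check of normality, and neither branch estimates the 2x2 effects

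*Combined protocol and SAP*

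**What the plan says.** The Statistical analysis section gives one rule for all continuous variables: "Statistical tests for continuous data were based on 1-way analysis of variance for normally distributed data, or the Kruskal-Wallis test for nonnormal data". The next sentence explains how normality is judged: "This is determined by histogram plots and Levene test". It gives no cut-off, no order of precedence between the two tools, and no version of Levene's test.

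Under Outcomes, the primary outcome is time in seconds from T0 to T3. No separate frequentist test is named for it, so the general rule applies. Study design describes a 2x2 trial of position and insufflation. The Sample size analysis section bases its number on analysis of variance and adds: "We will evaluate for the presence of interaction between the different interventions as two interventions are employed at the same time". It also plans a Bayesian analysis of every outcome, without naming a likelihood or a scale.

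**The concern.** Levene's test asks whether groups have equal spread. It does not ask whether the data are normal. Used as a normality check it can fail in two ways: equally skewed arms can pass it, and normal arms with unequal spread can fail it.

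The second failure matters most here. The plan's target distribution is narrower than its reference distribution as well as lower, so a treatment that works as hoped makes the variances differ. The treatment effect can then decide which test is run.

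Three things are at stake: whether the primary frequentist test is fixed before the data are seen, whether it is the test behind the sample size, and whether it answers the factorial question.

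**Working it through.** **Inputs (Sample size analysis).** Reference median 168 s, IQR 86-286; target median 108 s, IQR 69-160; 28 per arm; two-sided alpha 0.05; power 80%. No SD and no distribution is given, so both are assumptions below.

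**The plan's own number.** The plan states "28 subjects in each arm for a total of 112 subjects would be needed to detect an effect size of > 60 seconds". Taking SD = IQR/1.349:
- reference: (286 - 86)/1.349 = 148.3 s
- target: (160 - 69)/1.349 = 67.5 s
- pooled: sqrt((148.3² + 67.5²)/2) = 115.2 s

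A factorial main effect of 60 s needs 2 x (1.960 + 0.842)² x (115.2/60)² = 57.9, so 58 per level or 29 per cell. That is close to 28. A four-group omnibus ANOVA at the same SD needs 42 to 82 per arm, depending on the pattern of means. The 28 therefore cannot be uniquely reproduced, but this point does not depend on it.

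**Is skewness likely?** Quartile skewness = (Q3 + Q1 - 2 x median)/(Q3 - Q1).
- reference: (286 + 86 - 336)/200 = 0.18
- target: (160 + 69 - 216)/91 = 0.14

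Both are right-skewed.

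**Assumed shapes.**
- Lognormal: stated medians, log SD = ln(286/86)/1.349 = 0.891 and ln(160/69)/1.349 = 0.623. With medians fixed, the implied quartiles are 92-306 and 71-164, so the match is approximate.
- Gamma fitted to the quartiles: shape 1.54 and 2.86; medians 166 and 108.

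**Simulation.** Four arms of 28, 10,000 trials per scenario (Shapiro-Wilk on 1,000). Null: four identical arms, range over reference and target shapes. Effect: two arms at reference and two at target, a pure position effect. Gated means Kruskal-Wallis if Levene rejects, otherwise ANOVA; histograms are left out.

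| Rejection rate | Null, lognormal | Null, gamma | Effect, lognormal | Effect, gamma |
|---|---|---|---|---|
| Levene, median-centred | 4% | 4-5% | 75% | 93% |
| Levene, mean-centred | 19-28% | 12-17% | 95% | 98% |
| Shapiro-Wilk on residuals | 100% | 99-100% | 100% | 100% |
| One-way ANOVA | 4-5% | 5% | 82% | 89% |
| Kruskal-Wallis | 5% | 5% | 68% | 65% |
| Gated | 3-4% | 4% | 67% | 65% |
| ANOVA and Kruskal-Wallis disagree | 4-6% | 3-4% | 20% | 24% |

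Repeat runs moved these figures by up to about 3 points.

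**The opposite failure.** With normal data and SDs of 148.3 and 67.5 s, Levene rejects in 99% of trials, so normal data would be labelled nonnormal.

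**Another pattern of effect.** If only one of the four arms improves, ANOVA against Kruskal-Wallis is about 50% against 56% (lognormal) and 65% against 52% (gamma). The choice of test matters, but its direction depends on the unknown shape.

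**What each branch delivers.** One-way ANOVA and Kruskal-Wallis each give a single 3-df comparison of four groups. Neither gives a position effect, an insufflation effect or an interaction.

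**The case against.** **The rule also names histograms.** A reader might infer that the rule cannot detect skewness. The documents do not support that: histograms can show it, and with skewness this strong they probably would. The gated figures hold only if Levene decides. What remains is that visual inspection has no criterion and no stated precedence, so the choice is made after the data are seen.

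**Levene may have been meant for ANOVA's equal-variance assumption.** That is a sensible reading, but the text ties both tools to the normal/nonnormal decision and says nothing about variances.

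**The power loss is not peculiar to Levene.** This stands. A working normality test would flag these data in 99-100% of trials and also lead to Kruskal-Wallis, at 65-68% power. The shortfall belongs to that branch.

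**A pre-specified log-scale model might seem to recover the loss.** A reader might set about 67% for the gated test against about 85% for a log-scale position effect and call the gap the cost of the gate. That compares a 3-df test with a 1-df test: a log-scale one-way ANOVA reaches only 71%. The advantage also needs lognormal data. Under the gamma shape the log-scale position effect has about 65% power, the same as the gated test.

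**No false-positive harm.** This stands: the gated rule rejects in 3-4% of null trials.

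**Other analyses are planned.** The interaction evaluation and the Bayesian analysis are not said to depend on the rule, so the 2x2 question is not abandoned. But neither has a stated model, so they do not repair the frequentist rule. The missing factorial terms affect the ANOVA branch equally, so Levene does not cause that gap.

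**Conclusion.** The rule is wrong as written and should be changed. Its only formal test addresses variance, its visual part has no criterion, and both tests it can select leave the position, insufflation and interaction effects unestimated.

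If Levene decides, the median-centred version flags equally skewed arms at about its nominal rate, while the planned position effect triggers the switch in about 75-98% of trials. In those effect scenarios the two tests disagree in about 20-26% of trials, and omnibus power is about 65-68% instead of 80%. These sizes rest on the assumed lognormal and gamma shapes, on 28 evaluable patients per arm, and on a gate that ignores the histograms. That Levene's test does not assess normality needs no simulation.

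The harm is to pre-specification, to agreement with the sample-size basis and to interpretability. Validity under the null is not affected.

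**What to change.** For the primary outcome, delete the histogram/Levene gate. Pre-specify one model of completion time (T0 to T3) with position, insufflation and their interaction, and standard errors that allow unequal variances.

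Fix the scale in advance. Seconds is a reasonable choice because the target is stated in seconds, with log time as a sensitivity analysis. Power does not settle the scale. In the position-effect scenario, the main effect in seconds with unequal-variance errors has 95-97% power and the log-scale effect 65-86%, but the 60 s in the plan is a difference in medians (168 - 108). The corresponding differences in means are larger: 209 - 122 = 87 s under gamma and 250 - 131 = 119 s under lognormal. The SAP should say which of these the model targets.

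Keep Levene's test, if wanted, as a variance diagnostic, and Kruskal-Wallis as a descriptive check. The cost is SAP wording only; allocation, data collection and the planned 136 patients do not change.
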